4.3. Justification of the Dose and Schedule

4.3.1. AV7909

The AV7909 formulation, dose, route of administration and dosing schedule being used in this study are the same as those being used in the licensure-enabling clinical trial being conducted concurrently ([Study EBS.AVA.212](#)). The formulation of 0.5 mL AVA and 0.25 mg CPG 7909, administered IM as two 0.5 mL doses, 2 weeks apart, was selected for further development based on the following observations in two previously conducted AV7909 clinical trials {[Hopkins et al, 2013](#); [Hopkins et al, 2016](#)}.

- Keeping the AVA content at 0.5 mL (compared to 0.25 mL) maintained immunogenicity
- Increasing the CPG 7909 content beyond 0.25 mg to 0.5 mg increased the incidence and severity of both local and systemic reactions as assessed with a participant e-diary without enhancing immunogenicity
- Injection site reactogenicity was similar to that observed for BioThrax
- At 0.25 mg CPG 7909, a lower amount of unbound CPG could potentially reduce the risk of off-target immune activation

4.3.2. Ciprofloxacin

The ciprofloxacin dose (500 mg), dosing schedule [twice a day (q 12 hr)] and route of administration [by mouth (po)] being used in this study are those that would be used for PEP in the event of anthrax exposure and similar to those that were used in the prior PEP study conducted with ciprofloxacin and BioThrax {[EPDG, 2014](#)}. In this study and the prior BioThrax study (Study EBS.AVA.009), ciprofloxacin administration occurs on an intermittent daily rather than a continuous daily dosing schedule, with the assumption that intermittent dosing would achieve the required single dose and steady state concentrations needed prior to and following the vaccination schedule, as well as the immunogenicity endpoints while restricting the antibiotics administered to the minimum to achieve these ends.

Ciprofloxacin will be administered intermittently in three courses that will be used both by site staff for in-clinic visits and by participants when they are at home. The course format in terms of number of tablets and when participants will receive each course will be described in the Pharmacy Manual.

In addition to ensuring the achievement of steady state concentrations before and after the complete two-dose series of the vaccine, the selected ciprofloxacin dosing periods reflect the time when the inflammatory and immunosuppressive effects of ciprofloxacin are most likely to affect the antibody response to AV7909 {[Takahashi et al, 2005](#); [Kaminski et al, 2010](#)}. The

AV7909 Anthrax Vaccine

IND 014451

Protocol EBS.AVA.210, Version 3.0 (28 October 2019)

intermittent dosing schedule was chosen in the hopes of minimizing any adverse effects from ciprofloxacin. This strategy appeared to have been successful in the BioThrax plus ciprofloxacin study in that ciprofloxacin-related AEs were low in number, frequently reported as related to both ciprofloxacin and BioThrax, generally mild in severity and resolved without sequelae by the end of the study {EPDG, 2014}.

4.3.3. Doxycycline

The doxycycline dose (100 mg), dosing schedule [twice a day (q 12 hr)] and route of administration [by mouth (po)] being used in this study are those that would be used for PEP in the event of inhalation exposure to anthrax. As with ciprofloxacin, doxycycline administration will occur on an intermittent daily rather than a continuous daily dosing schedule for the same reason this approach is used for ciprofloxacin. This schedule will provide the required single dose and steady state PK dosing regimens needed and, in addition to achieving the needed steady-state concentrations before and after vaccination, is designed to achieve the immunogenicity end-points while restricting the antibiotics administered to the minimum required to achieve these ends.

However, since the half-life of doxycycline is considerably longer than that of ciprofloxacin (15-16 hours after a single dose and 22 or more hours after multiple doses compared to 3-7 hours for ciprofloxacin), participants in Group 2 will receive a few more doses of antibiotic than those in Group 1. This is because we believe more days of dosing will be required to achieve steady state. Thus, Group 2 will receive seven days of dosing with doxycycline compared to five days used for ciprofloxacin before tests for steady state are applied.

Doxycycline will also be administered in three courses that will be used both by site staff for in-clinic visits and by participants when they are at home. The format of the courses in terms of number of tablets and when participants will receive each course will be described in the Pharmacy Manual.

The doxycycline dosing periods were chosen because they have been shown to have an effect on humoral immunity in mice {Woo et al, 1999} and to affect post-vaccination cell-mediated immunity in swine {Pomorska-Mól et al. 2014}, suggesting it could also affect the antibody response to AV7909. The intermittent dosing schedule was chosen in the hopes of minimizing any adverse effects from doxycycline.

4.4. End of Study Definition

A participant is considered to have completed the study if he or she has completed all phases of this study through the 12-month final safety follow-up phone contact (ie, Day 388 ± 14 d). Participants who do not complete the study are considered to have been withdrawn from the trial (refer to Section 7.3).

The End of Study Date is defined as the date of the last participant's final safety follow-up call, or earlier if the participant's last follow-up contact occurs before this time point.

AV7909 Anthrax Vaccine

IND 014451

Protocol EBS.AVA.210, Version 3.0 (28 October 2019)

5. STUDY POPULATION

Participants will be recruited at up to five clinical research centers in the United States. At least 210 healthy adults meeting the eligibility criteria will be randomized 1:1:1 to one of the three IP groups: 70 in Group 1 (AV7909 + ciprofloxacin), 70 in Group 2 (AV7909 + doxycycline) and 70 in Group 3 (AV7909 alone). Groups 1 and 2 will each have two subgroups; the A subgroup (N=40) will undergo PK sessions while the B subgroup (N = 30) will not. Approximately the first 40 participants who are randomized into Groups 1 and 2 will be assigned to Treatment Group 1A or Group 2A, while those who are randomized into Groups 1 and 2 thereafter will be assigned to Groups 1B or 2B.

No waivers of inclusion and/or exclusion criteria will be permitted in the trial. The sites will be asked to implement procedures that will ensure a representative racial distribution among recruited participants and result in populations that are gender- and age-balanced (ie, between 40-60% male with 40-60% of participants in the two age ranges of 18-30 years of age and 31-45 years of age).

5.1. Inclusion Criteria

Individuals must meet all of the following inclusion criteria for study participation:

1. Written informed consent obtained from the participant (dated, signed, and captured in the medical chart at the site).
2. A male or female, aged 18 to 45 years of age, inclusive, at the time of informed consent.
3. Healthy condition as established by medical history and clinical examination before entering into the study.
4. Have a body mass index (BMI) less than or equal to 35.0 kg/m² at the Screening visit.
5. Have adequate venous access for phlebotomies.
6. For a woman of childbearing potential (WOCBP), negative pregnancy test at Screening and pre-randomization on Day 1, not currently breastfeeding, and no intention to become pregnant during the study period through 12 months after last receipt of any investigational product (IP).

Every female participant is considered to be a WOCBP unless she is surgically sterile (ie, has had a hysterectomy, bilateral salpingectomy or bilateral oophorectomy) or postmenopausal [which is defined as >12 consecutive months without menses and a Screening FSH of >30 mIU/mL]. Adequate birth control (as defined here) must be initiated at least one month prior to randomization on Day 1 and used throughout the trial. Adequate birth control methods are sexual abstinence, intrauterine device/system (IUD/IUS), birth control pills, implantable or injectable contraceptives (eg, Norplant[®] or Depo-Provera[®]), removable birth control device (eg, NuvaRing[®] or Evra[®] patches) or double-barrier method of birth control (diaphragm in combination with contraceptive jelly or condoms in conjunction with contraceptive jelly, cream or foam), tubal ligation, or have a monogamous relationship with vasectomized partner who has been vasectomized for 6 months or more prior to the participant's trial entry.

AV7909 Anthrax Vaccine

IND 014451

Protocol EBS.AVA.210, Version 3.0 (28 October 2019)

Female participants randomized to Groups 1 or 2: be willing to add a double-barrier method, IUD, or abstinence as back-up forms of birth control since ciprofloxacin and doxycycline may decrease the effectiveness of birth control pills, implantable or injectable contraceptives.

5.2. Exclusion Criteria

Individuals meeting any of the following exclusion criteria will be excluded from study participation:

1. A Screening clinical laboratory test result greater than the central laboratory's upper limit of normal (ULN) for aspartate aminotransferase (AST), alanine aminotransferase (ALT), random glucose, total bilirubin, blood urea nitrogen (BUN), or creatinine. Other serum chemistry parameters that are not within the reference range will not be considered exclusionary unless deemed clinically significant by the principal investigator.
2. History of allergic reaction or intolerance to quinolone antimicrobials or any medical condition that would contraindicate the use of ciprofloxacin, including and not limited to vascular disorders, tendon disorders, certain genetic connective tissue disorders (eg, Marfan and Ehlers–Danlos syndrome), prolongation of QT interval, seizures, peripheral neuropathy, increased risk of *C. difficile* infection (see ciprofloxacin prescribing information in the Pharmacy Manual).
3. History of allergic reaction or intolerance to tetracycline antibiotics or any medical condition that would contraindicate the use of doxycycline including an increased risk of *C. difficile* infection, increases in BUN or an increased sensitivity to direct sunlight or ultraviolet radiation resulting in erythema (see doxycycline prescribing information in the Pharmacy Manual).
4. Has a need for any of the prohibited medications in [Section 6.5.1](#) or requires the medications/foods within the prohibited times in [Section 5.3.1.1](#).
5. Have a tattoo/scar/birthmark or any other skin condition affecting the deltoid area that may interfere with injection site assessments.
6. History of anthrax disease, suspected exposure to anthrax, or previous vaccination with any anthrax vaccine.
7. Have previously served in the military any time after 1990 or plan to enlist in the military any time from Screening through the final telephone contact.
8. Previous anaphylactic reaction, severe systemic response, or serious hypersensitivity to a prior immunization or a known allergy to synthetic ODNs, aluminum, formaldehyde, benzethonium chloride (phemerol).
9. Plan to have an elective surgery at any point during the study until after the final safety phone contact.
10. Have donated or plan to donate blood within one month prior to enrollment or at any point during the study until after the final safety phone contact.

AV7909 Anthrax Vaccine

IND 014451

Protocol EBS.AVA.210, Version 3.0 (28 October 2019)

11. Use of any investigational or non-registered product (drug, vaccine or biologic) within 30 days preceding the dose of study vaccine, or planned use during the study until after the final safety phone contact.
12. Planned administration of any commercially-available vaccine from one week prior to the first study vaccination through two weeks after the last vaccination.
13. Have experienced chronic dosing (defined as more than 14 days) with any immune-modifying drugs within six months of study enrollment. This includes oral, intramuscular, intra-articular, intravenous, or inhalation corticosteroids except in the case of inhaled or intranasal medications for seasonal allergies (see [Table 3](#)).
14. Receipt of immunoglobulins and/or any blood products within the three months preceding study enrollment or at any point during the study period until after the final safety visit on Day 51.
15. An abnormal electrocardiogram (ECG) at screening interpreted as ‘Abnormal, Significant’. Inclusion of participants with ‘Abnormal, Insignificant’ ECGs will be based on the principal investigator’s discretion.
16. Have an active malignancy or history of metastatic or hematologic malignancy.
17. Have a history of an autoimmune, inflammatory, vasculitic or rheumatic or rheumatic disease including but not limited to systemic lupus erythematosus, Guillain-Barré syndrome, myasthenia gravis, polymyalgia rheumatica, diabetes mellitus type I, rheumatoid arthritis or scleroderma.
18. A positive laboratory evidence of hepatitis B, hepatitis C, or human immunodeficiency virus (HIV) HIV-1 or HIV-2 infection.
19. Positive result on urine drug screen, any evidence of ongoing drug abuse or dependence (including alcohol), or recent history (over the past five years) of treatment for alcohol or drug abuse.
20. Has an acute disease at the time of enrollment.

Note that screening lab tests may be delayed to allow the resolution of a transient acute condition or the subject may be rescreened according to procedures under [Section 5.4](#).
21. Any medical condition that, in the opinion of the investigator, could adversely impact the participant’s involvement or the conduct of the study.
22. Have a significant chronic condition (see Sponsor’s guidance on significant chronic conditions in [Appendix C](#)), eg, serious cardiovascular, pulmonary, hepatic, type II diabetes mellitus or renal disease that, in the opinion of the investigator, would render treatment unsafe or would interfere with trial evaluations or completion of the study.
23. An opinion of the investigator that it would be unwise to allow the participant to be randomized into the study.
24. Member or immediate family member of an investigator site team.

AV7909 Anthrax Vaccine

IND 014451

Protocol EBS.AVA.210, Version 3.0 (28 October 2019)

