Two participants in Study EBS.AVA.208 discontinued vaccination because of mild generalized pruritus and rash (AV7909 Arm 2) and moderate rash (AV7909 Arm 1), all events considered to be related to study product administration. Both Arm 1 and Arm 2 received two doses of AV7909 containing 0.5 mL AVA + 0.25 mg CPG 7909; however, for Arm 1, the doses were delivered two weeks apart and for Arm 2, the doses were delivered 4 weeks apart {[Hopkins et al, 2016](#)}. In Study V011, which consisted of three treatment groups [AVA (0.5 mL) alone, CPG 7909 (1.0 mg)-alone and AVA (0.5 mL) + CPG 7909 (1.0 mg)] all administered as three doses two weeks apart, two participants in the AVA + CPG 7909 arm had hypersensitivity reactions. Both of these were considered by the investigator to be unlikely related to study product administration. An additional participant in the AVA + CPG 7909 group discontinued vaccination after the second injection due to the development of moderate generalized rash (accompanied by pruritus) that was considered to be related to study product administration {[Coley, 2006](#)}. Appropriate medical treatment and supervision must be available to manage possible anaphylactic reactions following administration of the vaccine.

AV7909 Anthrax Vaccine

IND 014451

Protocol EBS.AVA.210, Version 3.0 (28 October 2019)

AV7909 is not to be administered to participants with known sensitivity to any of the vaccine components, eg, synthetic ODNs, formaldehyde, benzethonium chloride (phemerol), or aluminum, or a sensitivity to latex.

No participants in the completed AV7909 clinical trials or in CPG 7909-adjuvanted infectious disease trials have reported AEs related to autoimmune disorders, although several have reported positive, transient and/or non-symptomatic findings for clinical laboratory markers of disease such as anti-nuclear antibodies (ANA), anti-double-stranded deoxyribonucleic acid (anti-dsDNA) antibodies, and rheumatoid factor (RF). In oncology trials of CPG 7909 (reviewed in the AV7909 Investigator's Brochure) that typically use higher doses and treatment durations than expected with AV7909 vaccine exposure, autoimmune disease has been reported in multiple participants, although causal attribution to the study product is complicated by comorbidities and concomitant products/therapies. Autoimmune conditions have included polyarthralgia, arthritis, Sjögren's syndrome, autoimmune thyroiditis, vitiligo, Guillain-Barré syndrome, and ulcerative colitis.

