6. TREATMENTS

6.1. Treatment Administration

6.1.1. AV7909 Description

AV7909 is a preformulated, sterile, milky-white suspension for IM injection consisting of the AVA drug substance (AVA) and CPG 7909 adjuvant. All participants will receive one dose of AV7909 0.5 mL IM, consisting of 0.5 mL AVA and 0.25 mg CPG 7909, on Day 8 and one dose IM on Day 23.

The AV7909 vaccine, manufactured by [REDACTED], will be supplied in 6 mL (nominal fill volume) clear borosilicate glass multi-dose vials with rubber stoppers and flip-top aluminum seals for storage. A single vial is filled with approximately 6.1 mL. For purposes of this trial, only a single dose (0.5 mL) will be used from each vial.

Each vial will be labeled with the name, main constituents and volume of study product; route of administration; manufacturer name; characterization as “sterile” product and “multi-dose vial”; storage conditions; manufacturing (fill) date and lot number; and appropriate federal caution statement for investigational use product.

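### Section 2.3.2.3 bars AV7909 for anyone with a latex sensitivity, but exclusion criterion 8 omits latex, so screening against the criteria does not prompt sites to ask about it

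*Protocol*

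**What the plan says.** Protocol Section 2.3.2.3, on the risks of AV7909, states that "AV7909 is not to be administered to participants with known sensitivity to any of the vaccine components". It gives examples of components and then adds latex as a separate item; the list ends "benzethonium chloride (phemerol), or aluminum, or a sensitivity to latex".

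Exclusion criterion 8 appears in the same terms in the synopsis and in Section 5.2. It has two limbs. The first is "Previous anaphylactic reaction, severe systemic response, or serious hypersensitivity to a prior immunization". The second is "a known allergy to synthetic ODNs, aluminum, formaldehyde, benzethonium chloride (phemerol". Latex is in neither.

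Section 5 makes the criteria binding: "No waivers of inclusion and/or exclusion criteria will be permitted in the trial".

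**The concern.** The protocol identifies a group that must not receive the vaccine, and the list that sites apply before randomisation leaves that group out. Criterion 8 writes out the other named sensitivities and does not leave them to judgement, and nothing in either document explains treating latex differently.

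What is at stake is participant safety and avoidable exposure. A healthy volunteer with a latex sensitivity could be randomised and, in Groups 1 and 2, start an antibiotic before anyone notices that Section 2.3.2.3 rules out the vaccine. If the history never comes out, the vaccine is given to someone that section says should not have it.

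**Working it through.** No calculation applies beyond a count, so the check is a comparison of texts.

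**1. The two lists side by side.**

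| Sensitivity named | Section 2.3.2.3 | Criterion 8 (synopsis and Section 5.2) |
|---|---|---|
| Synthetic ODNs | yes | yes |
| Formaldehyde | yes | yes |
| Benzethonium chloride | yes | yes |
| Aluminum | yes | yes |
| Latex | yes | no |

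Five are named in one place and four in the other: 5 − 4 = 1, and the missing one is latex. The components in Section 2.3.2.3 are offered as examples, so that part of the list is open-ended. Latex stands apart from it as its own item, so the open wording does not account for the omission.

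**2. Whether latex is named elsewhere in the rules.** It is not in any of the other 23 exclusion criteria, in the vaccination rules of Section 6.1.4, or in the discontinuation criteria of Table 4.

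**3. Which checks depend on the criteria.** The reviews in Section 8.1.1.1 (Screening) and Section 8.1.1.2 (Day 1, before randomisation) are expressly made against the inclusion and exclusion criteria. Those two therefore carry no prompt about latex. The later reviews before vaccination 1 are worded more generally: eligibility for vaccination in Sections 8.1.2.5 (Group 1A) and 8.1.4.4 (Group 2A), and simply eligibility in Sections 8.1.3.2, 8.1.5.2 and 8.1.6.1. Section 2.3.2.3 could properly be brought to bear at those.

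**4. What follows, by when the sensitivity comes to light.**

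- *Screening or Day 1, before randomisation:* the investigator can exclude on judgement. No study product has been taken.
- *Groups 1 and 2, after antibiotic has started (Day 4 and Day 2 respectively) but before vaccination 1:* if the investigator judges vaccination unsafe, Section 6.1.4 requires withdrawal with no rescreening. Section 7.3 adds that withdrawn participants are not replaced.
- *Group 3, before vaccination 1:* nothing has been taken, and Section 6.1.4 allows re-screening.
- *Any group, after vaccination 1:* under Section 6.1.4, someone who cannot have vaccination 2 in its window stays in the study for safety follow-up; Sections 7.3 and 7.3.1 say the same in substance.
- *Never:* the remaining safeguards are the 30-minute observation after vaccination and Table 4 item 2, and both act only after exposure.

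**5. The hazard itself.** Section 6.1.1 describes "multi-dose vials with rubber stoppers and flip-top aluminum seals for storage". It does not say whether the rubber contains latex. Neither document gives the number of latex-sensitive volunteers expected.

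**The case against.** The best reply is that the practical gap is narrow. A full medical history is taken at Screening and updated on Day 1. An investigator who hears of a latex sensitivity has a protocol that forbids giving that person the vaccine, and two criteria that allow exclusion: number 21, "Any medical condition that, in the opinion of the investigator, could adversely impact" the participant's involvement or the study, and number 23, "An opinion of the investigator that it would be unwise to allow the participant to be randomized into the study". Section 6.1.4 adds a further stop before vaccination 1. The Investigator's Brochure and Pharmacy Manual, which may describe the closure, are not available here.

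Much of this stands. What remains is the latex history that nobody elicits because no criterion prompts the question. The clauses relied on rest on the investigator's opinion, whereas Section 2.3.2.3 is unconditional. The first limb of criterion 8 helps only for people who have already reacted to an immunization. Because latex is not a criterion, the no-waiver rule does not reach it, and Table 4 item 5, on eligibility violations found after randomisation, is not engaged. Naming latex would bring both into play, although item 5 would still need the principal investigator's determination and the Medical Monitor's agreement.

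**Conclusion.** The inconsistency is real and worth correcting as a matter of participant safety. One sensitivity that the protocol treats as a bar to vaccination is missing from the exclusion list, and the two reviews tied expressly to that list do not raise it.

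Three stronger conclusions might be inferred, and the documents do not support them.

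- *That latex-sensitive people may be vaccinated.* They may not: Section 2.3.2.3 still bars dosing once the sensitivity is known.
- *That every review before vaccination 1 is blind to latex.* This is firm only for Screening and Day 1.
- *That participants face a known allergic risk, or one measured by the antibiotic doses taken before discovery.* The latex content of the stopper is not stated, so the size of the hazard is unknown, and antibiotic doses say nothing about it.

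No endpoint, power or type I error is affected. The conclusion rests on the current protocol text alone and assumes that no unseen site document already adds a latex question.

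**What to change.** Add latex sensitivity to the second limb of exclusion criterion 8, in both the synopsis and Section 5.2, and include a question about it in the screening history. If instead the sponsor can confirm that the product and its closure contain no latex, delete latex from Section 2.3.2.3. Either way the two lists should agree.

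The first route costs one phrase in two places and one screening question, with possibly a few more screen failures among people the protocol already says should not be vaccinated. The second costs one deleted phrase. Neither touches the analysis.
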